Target number of participants	We anticipate to recruit 800 participants for this study over the course of 4 years

Criteria for evaluation	
Primary outcome measure(s): The primary outcome of the study is to evaluate if specific heritable arrhythmic disorders are associated with changes in selected protein distribution/expression levels at cell-cell junctions within the buccal mucosa. Our preliminary studies suggest that protein distribution/expression alterations in the buccal mucosa mirror equivalent changes that occur in the myocardium of patients with ACM. This study will evaluate the use of this "novel diagnostic tool" in individuals at risk of sudden cardiac death due to other, more common forms of arrhythmic disorders including the cardiac channelopathies. The processing approach (laboratory technique: immunocytochemistry) for protein distribution visualization has been optimized to be qualitative rather than quantitative. In this sense - each sample will be characterized by "presence" or "absence" of a specific protein at the cell-cell connections. We deem that the qualitative approach is not subject to bias and will ensure accuracy and reproducibility of the results.
 
Secondary outcome measure(s): A potential secondary outcome of the research is whether we can correlate protein distribution in the buccal mucosa with specific genotypes. Our preliminary results on the cohort of patients with ACM suggest that mutations in different genes result in different protein distribution patterns within the buccal mucosa. Being able to predict the gene bearing the disease-causing mutation will significantly reduce the time and cost of genetic sequencing. Identifying the specific gene underlying a heritable arrhythmic disorder is of pivotal importance as increasingly developing genotype/phenotype correlations help individualized risk identification and patient management.
 
Another potential secondary outcome of the research has to do with the effect changes in the patients' treatment plans may have on protein distribution. An example has to do with a protein known as Connexin43 (Cx43). Cx43 is the major gap junction protein expressed in the heart and is responsible for the electrical coupling of the cells and the smooth propagation of electricity throughout the myocardium. Cells at the buccal mucosa also express Cx43. It has been shown that patients with arrhythmic disorders show decreased distribution of Cx43 at the cell borders in their hearts and this "Cx43 remodeling" has been associated with an increased risk for arrhythmias. Our preliminary studies show that patients with ACM, as well as patients with different types of cardiomyopathy (including dilated, hypertrophic and ischemic) show Cx43 remodeling in their buccal mucosa. If a patient shows Cx43 remodeling during initial sampling and in a follow-up visit his clinical care team deems necessary to change his treatment plan (for instance, if he/she is to be started on a different anti-arrhythmic drug) we would like to study Cx43 distribution again during one of his/hers follow up visits. If the new treatment plan results in restoration of Cx43 at the buccal mucosa cell connections, and given how protein distribution in the buccal epithelium mirrors protein distribution in the heart, this finding may be an indication of successful arrhythmia management. It could thus, potentially, provide us with a non-invasive, straightforward and risk-free means to assess therapy efficacy in the future.

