Both for the primary study (buccal smear immunostaining) and the sub-study (buccal cell western immunoblotting) only frequencies and associations will be assessed. No complex statistical analysis is required for completion of this study. Differences between disease groups in the distribution of immunoreactive signals and levels of protein expression will be assessed in a pairwise fashion with the Fisher exact test. Bonferroni correction will be used to correct P values because of multiple comparisons as appropriate. A p value of less than 0.05 will be considered significant. SPSS 21.0 software shall be used for all analyses. This statistical analysis will be performed by [name]. If expert statistical help is required, the research team will consult medical statisticians within St. George's University of London ([name] [name]) who shall not have access to the participants' personal information.

To describe the precise methods of analysis, I shall use ACM as an example. We have previously shown that in the hearts of patients with ACM a protein known as plakoglobin is dislocated from the cell-cell junctions regardless of the underlying pathogenic mutation or even in cases where no mutation has been identified but the clinical or pathological examination are consistent with a diagnosis of ACM. We used the "presence" or "absence" of plakoglobin from the cell junctions in the buccal mucosa to predict which individuals had ACM in a blinded fashion. Of 39 patient samples obtained, plakoglobin was absent from the cell junctions in 34. It was not, however, absent in samples from patients diagnosed with other forms of cardiomyopathy including hypertrophic, dilated or ischemic cardiomyopathy. This indicated that using plakoglobin distribution in the buccal mucosa as a means to diagnose ACM had sensitivity of 87.1% and specificity of 100%.

Secondary endpoint analysis

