Regarding the secondary outcome of the analysis: patients with ACM bear mutations in genes encoding desmosomal proteins. These include desmoplakin, desmoglein2, desmocollin2, plakoglobin and plakophilin2 (PKP2). Buccal cells do not express PKP2. Instead they express a different isoform of the protein; plakophilin1 (PKP1). 15/15 ACM patients bearing mutations in PKP2 showed loss of PKP1 signal in their buccal mucosa. No patients bearing mutations in different genes showed this abnormality. Moreover, only patients bearing mutations in desmoplakin, desmoglein2 or desmocollin2 showed loss of desmoplakin signal in their buccal mucosa. Accordingly, using PKP1 distribution to predict the presence of mutations in PKP2 showed 100% specificity and sensitivity. This is a remarkable finding given how PKP1 and PKP2 are expressed by different genes localized on different chromosomes. And yet, a mutation in one

isoform expressed in one tissue affects distribution of a different isoform expressed in a different tissue. Similarly, using desmoplakin distribution to predict the presence of mutations in desmoplakin, desmoglein2 and desmocollin2 showed 100% specificity and sensitivity. We are now at a position to use the same approach in other, more common forms of arrhythmic disorders including the cardiac channelopathies.

We shall use the presence or absence of signal for specific proteins at buccal smears to:

1. predict clinical diagnosis for heritable arrhythmic disorders
2. predict the genes bearing disease-causing mutations
3. assess the effect of potential changes in treatment plan on the distribution of proteins (specifically Cx43)

We shall use the expression levels of specific proteins to establish

1. If mutations act through haploinsufficiency
2. If anti-arrhythmic medication corrects the distribution of connexin43 by increasing its production levels.

Sensitivity and other planned analyses (if applicable)

Please see explanation above

Interim analysis

If following the first year of the study, it appears that we are unable to predict "arrhythmic status" using such samples, we shall stop recruiting patients with cardiac channelopathies and will only focus on patients with cardiomyopathies, where the correlation is already proved

Committees involved in the trial

A trial management group (TMG) will be in place throughout the duration of the study

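### Gene prediction: the 100% specificity for PKP1 is stated only against carriers of other mutations, so it is not shown to apply to patients who have not been sequenced

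*Combined protocol and SAP*

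**What the plan says.** The Primary endpoint analysis section offers the ACM pilot as a worked example of how the analysis will be done. The Secondary endpoint analysis section continues the example, says the same approach will be applied to other arrhythmic disorders, and lists gene prediction among its planned uses. No other method for gene prediction is given; the only test named is the pairwise Fisher exact test between disease groups.

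The pilot evidence on gene prediction is as follows.

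- PKP1 for PKP2 mutations: "15/15 ACM patients bearing mutations in PKP2 showed loss of PKP1 signal in their buccal mucosa", and "No patients bearing mutations in different genes showed this abnormality". From this, "using PKP1 distribution to predict the presence of mutations in PKP2 showed 100% specificity and sensitivity".
- Desmoplakin for three genes together: "only patients bearing mutations in desmoplakin, desmoglein2 or desmocollin2 showed loss of desmoplakin signal in their buccal mucosa", and then "Similarly, using desmoplakin distribution to predict the presence of mutations in desmoplakin, desmoglein2 and desmocollin2 showed 100% specificity and sensitivity".

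The Primary endpoint analysis section also notes, about the earlier heart-tissue work, that plakoglobin was displaced "even in cases where no mutation has been identified but the clinical or pathological examination are consistent with a diagnosis of ACM". The synopsis (Criteria for evaluation) gives the purpose: "Being able to predict the gene bearing the disease-causing mutation will significantly reduce the time and cost of genetic sequencing". The Secondary objectives section likewise describes steering sequencing towards proteins that look misplaced in the smear.

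**The concern.** Specificity depends on who counts as a negative. For PKP1 the only negatives mentioned are patients already known to carry a mutation in another gene. A test meant to direct sequencing will be used on people whose gene is unknown, and some of them will turn out to have no identifiable mutation. The pilot text reports no marker result for that group, and the plan gives no rule for handling it.

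If the study repeats the example as written, its specificity will be silent on whether mutation-negative patients also lose PKP1. Should some of them do so, the marker would point to PKP2 in patients in whom sequencing PKP2 finds nothing, and the reported accuracy would not show it.

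There are two smaller gaps. The statement that only carriers of the three genes lost desmoplakin speaks to specificity; nothing given here says that every such carrier lost it, so the 100% sensitivity has no visible count behind it. And none of the figures carries an interval.

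**Working it through.** **1. Reproducing the plan's figures.** PKP1 sensitivity is 15/15 = 100%, which agrees. PKP1 specificity and both desmoplakin figures cannot be recomputed, because no denominators are given.

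**2. Precision of what is given.** When all n of n are correct, the exact (Clopper-Pearson) two-sided 95% lower limit is 0.025^(1/n).

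- Sensitivity, n = 15: 0.025^(1/15) = 78.2%.
- PKP1 specificity with no false positives, by assumed number of comparators: 69.2% for 10, 83.2% for 20, and 85.8% for 24. The last is 39 − 15, if the 15 are among the 39 published ACM patients and all the others served as comparators, which the documents do not say.

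**3. What a carriers-only comparator can miss.** The documents give no marker result in mutation-negative patients, so this is an illustration. Assumed inputs:

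- share of tested patients with no mutation found, g = 30% or 50%;
- PKP2 share among mutation carriers = 45%;
- PKP1 lost in all PKP2 carriers and in no carrier of another gene, as in the pilot;
- fraction of mutation-negative patients who lose PKP1, f = 0, 10% or 30%.

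Per 100 tested:

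- g = 30%: 30 negative, 70 × 0.45 = 31.5 PKP2, 38.5 other gene.
- g = 50%: 50 negative, 50 × 0.45 = 22.5 PKP2, 27.5 other gene.

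Specificity = (other + neg × (1 − f)) / (other + neg). Positive predictive value (PPV) = PKP2 / (PKP2 + neg × f).

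| f | g | Specificity | PPV |
|---|---|---|---|
| 0 | 30% or 50% | 100% | 100% |
| 10% | 30% | 65.5/68.5 = 95.6% | 31.5/34.5 = 91.3% |
| 10% | 50% | 72.5/77.5 = 93.5% | 22.5/27.5 = 81.8% |
| 30% | 30% | 59.5/68.5 = 86.9% | 31.5/40.5 = 77.8% |
| 30% | 50% | 62.5/77.5 = 80.6% | 22.5/37.5 = 60.0% |

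Under these assumptions a comparison restricted to carriers of other genes reads 100% in every row.

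**4. Sensitivity to the PKP2 share.** With 15/39 = 38.5% in place of 45%, specificity is 95.9% and 93.8% at f = 10%, and 87.7% and 81.4% at f = 30% (g = 30% and 50% respectively). The pattern does not depend on the 45%.

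**The case against.** Several points on the other side stand.

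- A reader might infer that both markers were judged only against carriers of other genes. The text does not support that for desmoplakin. Its statement that only carriers of the three genes lost signal is not limited in that way and, read literally, would cover mutation-negative patients too. There the comparator is undefined rather than restricted.
- A reader might infer that the 100% is wrong for unsequenced patients. No document shows that mutation-negative patients lose signal, and if none do (f = 0) the figure stands. It is unproven for them, not refuted.
- A reader might infer that the plan excludes mutation-negative participants. It sets no such rule. They are eligible, and whether a mutation is known is on the data collection form. The gap is an unspecified denominator combined with a worked example that uses a narrow one.
- Desmoplakin loss leaves three of the five desmosomal genes listed, so it does not name a single gene. That does not undermine its figure, which is openly stated for the three together, and a three-gene group still narrows sequencing.
- The percentages are pilot results, and the missing counts may be in the cited publication, which is not available here.
- A patient with no causal mutation would gain nothing from wider sequencing either, so added harm to that patient is not demonstrated. What is at stake is whether the reported accuracy holds for the intended use.

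Treating the example as mere background does not succeed, because the plan presents it as the method and carries it forward.

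**Conclusion.** The point holds in this form. For PKP1 the stated comparator is carriers of other mutations, with no number. For desmoplakin the comparator is not defined, and no count given here supports the 100% sensitivity. The plan reuses this approach for a test aimed at people not yet sequenced, while acknowledging ACM cases without an identified mutation. The 100% specificity is therefore not shown to apply to the intended users, and repeating the carriers-only comparison could not show whether it does.

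The size is unknown. The illustrated loss of specificity runs from nothing to about 19 percentage points (100% − 80.6%). It rests on assumed values for the mutation-negative share, the PKP2 share and the rate of signal loss, none of which the documents supply. The 78.2% lower limit for 15/15 needs no such assumption. Gene prediction is a secondary objective, so this should be corrected, but it does not threaten the primary analysis.

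**What to change.** In the Secondary endpoint analysis section:

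- Define the gene-prediction analysis set as all participants with completed gene testing, including those in whom no mutation was found. Keep untested participants out.
- Cross-tabulate each marker against four classes: PKP2; desmoplakin, desmoglein2 or desmocollin2 (reported as a three-gene group); another gene; none found.
- Report sensitivity with its count and exact 95% interval. Report specificity with exact 95% intervals twice: against carriers of other genes, and with the none-found class added.
- Show the none-found row separately as well, because failing to identify a mutation does not prove there is none.
- Give the desmoplakin sensitivity with its count, or drop it.

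The cost is SAP wording, one table and two form items. The data collection form described in the data protection impact assessment asks whether a mutation is known, but lists neither which gene nor whether testing was completed. The care team, who already complete that part of the form, would need to record both. No new samples are needed. The accuracy figures may become less favourable.

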17.1 Annual Progress Reports (APRs)

The Chief Investigator will prepare the APR in accordance with JREOSOP0043. Following review by the Sponsor the report will be sent to the REC. The APR is due for submission annually within 30 days of the anniversary date on which the favourable opinion was given by the Ethics committee, until the trial is declared ended.

1.2 Notification of Serious Breaches of GCP and/or the protocol

Any Protocol Deviations, Violations will be documented using JREODOC0061, and entered onto the Sponsor's log JREOLOG0005. Potential Serious Breaches and Urgent Safety Measures will be recorded both on the Sponsor's Log JREOLOG0005 and processed according to JREOSOP0012 and where necessary JREOSOP0032

A "serious breach" is a breach which is likely to effect to a significant degree:

- (a) The safety or physical or mental integrity of the participants of the trial; or
- (b) The scientific value of the trial.

The CI will notify the Sponsor immediately of any case where there exists a possible occurrence of a serious breach

Finance

The PI is funded by the British Heart Foundation as well as a private donation to cover the costs of the immunohistochemical and confocal microscopy analysis. The NHS is providing the study team with an annual stipend to cover the costs of the materials required to obtain the sample (soft brushes and microscope slides). There shall be no monetary gain for the participants or the medical care providers involved in the study.

Insurance and indemnity

City St George's, University of London holds insurance to cover participants for injury caused by their participation in the clinical trial. Participants may be able to claim compensation if they can prove that City St George's has been negligent. This includes negligence in the writing of the protocol, or selection of trial resources.

Where the Trial is conducted in a hospital, the hospital has a duty of care to participants. City St George's, University of London will not accept liability for any breach in the hospital's duty of care, or any negligence on the part of hospital employees. Hospitals selected to participate in this clinical trial shall provide clinical negligence insurance cover for harm caused by their employees and a copy of the relevant insurance policy or summary shall be provided to City St George's, University of London, upon request.

Participants may be able to claim compensation for injury caused by participation in this Trial without the need to prove negligence on the part of City St George's, University of London or another party.

If a participant indicates that they wish to make a claim for compensation, this needs to be brought to the attention of City St George's, University of London immediately.

Failure to alert City St George's, University of London without delay and to comply with requests for information by the sponsor or any designated Agents may lead to a lack of insurance cover for the incident.

IP and development policy

Unless otherwise specified in agreements, the following guidelines shall apply: All Intellectual Property Rights and Know How (IP) related to the Protocol and the Trial are and shall remain the property of the Sponsor excluding

- 1) Pre-existing IP related to clinical procedures of any Hospital.
- 2) Pre-existing IP related to analytical procedures of any external laboratory.

All contributors

shall assign their its rights in relation to all Intellectual Property Rights and in all Know How, not excluded above to the Sponsor and at the request and expense of the Sponsor, shall execute all such documents and do all such other acts as the Sponsor may reasonably require in order to vest fully and effectively all such Intellectual Property Rights and Know How in the Sponsor or its nominee.

shall promptly disclose to the Sponsor any Know How generated pursuant to this Protocol and not excluded above and undertake treat such Know How as confidential information jointly owned between it and the Sponsor

Nothing in this section shall be construed so as to prevent or hinder and medical professional from using Know How gained during the performance of the Trial in the furtherance of its normal business activities, to the extent such use does not result in the disclosure or misuse of Confidential Information or the infringement of any Intellectual Property Right of the Sponsor.

Publication policy

Publication: "Any activity that discloses, outside of the circle of trial investigators, any final or interim data or results of the Trial, or any details of the Trial methodology that have not been made public by the Sponsor including, for example, presentations at symposia, national or regional professional meetings, publications in journals, theses or dissertations."

All scientific contributors to the Trial have a responsibility to ensure that results of scientific interest arising from Trial are appropriately published and disseminated. The Sponsor has a firm commitment to publish the results of the Trial in a transparent and unbiased manner without consideration for commercial objectives.

To maximise the impact and scientific validity of the Trial, data shall be consolidated over the duration of the trial, reviewed internally among all investigators and not be submitted for publication prematurely. Lead in any publications arising from the Trial shall lie with the Sponsor in the first instance.

Before the official completion of the Trial,

All publications during this period are subject to permission by the Sponsor. If an investigator wishes to publish a sub-set of data without permission by the Sponsor during this period, the **Steering Committee** shall have the final say.

Exempt from this requirement are student theses that can be submitted for confidential evaluation but are subject to embargo for a period not shorter than the anticipated remaining duration of the trial.

Up to 180 days after the official completion of the Trial

During this period the Chief Investigator shall liaise with all investigators and strive to consolidate data and results and submit a manuscript for peer-review with a view to publication in a reputable academic journal or similar outlet as the Main Publication.

- The Chief Investigator shall be senior and corresponding author of the Main Publication.
- Insofar as compatible with the policies of the publication outlet and good academic practice, the other Investigators shall be listed in alphabetic order.
- Providers of analytical or technical services shall be acknowledged, but will only be listed as co-authors if their services were provided in a non-routine manner as part of a scientific collaboration.
- Members of the Steering Group shall only be acknowledged as co-authors if they contributed in other capacities as well.
- If there are disagreements about the substance, content, style, conclusions, or author list of the Main Publication, the Chief Investigator shall ask the Steering Group to arbitrate.

Beyond 180 days after the official completion of the Trial

After the Main Publication or after 180 days from Trial end date any Investigator or group of investigators may prepare further publications. In order to ensure that the Sponsor will be able to make comments and suggestions where pertinent, material for public dissemination will be submitted to the Sponsor for review at least sixty (60) days prior to submission for publication, public dissemination, or review by a publication committee. Sponsor's reasonable comments shall be reflected. All publications related to the Trial shall credit the Chief and Co-Investigators as co-authors where this would be in accordance with normal academic practice and shall acknowledge the Sponsor and the Funders.

Statement of Compliance

The trial will be conducted in compliance with the protocol, Sponsor's Standard Operating Procedures (SOPs), GCP and the applicable regulatory requirement(s).

The study conduct shall comply with all relevant laws of the EU if directly applicable or of direct effect and all relevant laws and statutes of the UK country in which the study site is located including but not limited to, the Human Rights Act 1998, the Data Protection Act 1998, the Human Medicines Regulations 2012, ICH GCP, the World Medical Association Declaration of Helsinki entitled 'Ethical Principles for Medical Research Involving Human Subjects' (2008 Version), the NHS Research Governance Framework for Health and Social Care (Version 2, April 2005).

This study will be conducted in compliance with the protocol approved by the REC and according to GCP standards. No deviation from the protocol will be implemented without the prior review and approval of the Sponsor and REC except where it may be necessary to eliminate an immediate hazard to a research subject. In such case, the deviation will be reported to the Sponsor and REC as soon as possible.

23 List of Protocol appendices

Not applicable to this protocol

24 References

